### Primary Outcome

- Transfers due to infection (% of discharges to a hospital due to infection)

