### Secondary Outcome

- All cause admissions (% of discharges to a hospital)

Other outcomes of interest include MDRO prevalence (MRSA, VRE, ESBL, CRE), antibiotic usage, and emergence of resistance (strain collection). Project PROTECT coordinators will work closely with the on-site study champions to collect data on measured outcomes. Additionally, data will be obtained from state and national datasets.

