#### Trial Outcomes

| Trial Outcomes  | Explanation  |
|---|--|
| Primary outcome:
Hospital transfer due to infection, among hospital transfers | If the resident was transferred from the nursing home to a hospital, was the transfer made because the patient had an infection? |
| Secondary outcome:
Hospital transfer, among transfers                         | If the resident was transferred from the nursing home, were they transferred to a hospital?                                      |

Other outcomes are found in the below table. At the time of the study conception, these were planned for secondary manuscript submissions.

| Other Outcomes   | Explanation   |
|--|---|
| Multidrug-resistant organism (MDRO) colonization   | Was a resident colonized with a multidrug-resistant organisms (MDROs): (MRSA, VRE, ESBL, CRE)                               |
| Hospital transfer due to infection, among hospital transfers in Long Stay and Short Stay Subsets | As in above table, but with analyses stratified by length of stay.  |
| Hospital transfer, among transfers in Long Stay and Short Stay Subsets                           | As in above table, but with analyses stratified by length of stay.  |
| Emergency Department Transfer due to Infection; overall and in Long Stay and Short Stay Subsets  | Probability that a resident is sent to the emergency department for an infection, overall and stratified by length of stay. |

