## Statistical Analysis

Main trial results will be based on as-randomized, unadjusted analyses using generalized linear mixed models logistic regression. All outcomes will be assessed similarly. Here, we use the example of the primary outcome: transfer to a hospital for an infectious diagnosis. Clustering within nursing home will be accounted for using random effects, which are added model terms that allow unique baseline rates for each nursing home, and are used to account for clustered randomization. Model terms will include individual-level data on arm, nursing home, outcome events, trial period (baseline vs. intervention) and an interaction term between trial period and arm. Trial results will be assessed through the interaction term, which measures the difference in log odds between the baseline and intervention period between the two arms. We can write a simple version of the model symbolically as:

$$\text{logit}(\Pr[R_{ij}]) = \log\left(\frac{\Pr[R_{ij}]}{1 - \Pr[R_{ij}]}\right) = \beta_0 + \beta_1 \text{Arm}_{ij} + \beta_2 \text{Period}_{ij} + \beta_3 \text{Arm}_{ij} * \text{Period}_{ij} + b_i$$

where  $i$  is a nursing home,  $j$  is a resident within the nursing home, and  $R_{ij}=1$  if the transfer has an infection diagnosis and 0 if not.  $\text{Arm}$  and  $\text{Period}$  are indicator variables and are = 0 for patients in a nursing home in the control arm or baseline period and 1 if in the intervention arm or period, respectively. The random effect,  $b_i$ , allows for different readmission rates at each nursing home, and accounts for the clustering within a given nursing home. The ultimate effect of the intervention is assessed by  $\beta_3$ . If it is negative with p-value < .05 (or 95% CI excluding 0), then we can conclude that the intervention reduces the risk of infectious transfer.

Subsequent analyses will include as-treated and covariate-adjusted models. Adjusted models will account for individual age, gender, comorbidities (by diagnostic codes), and functional status scores. All analyses will use current versions of SAS (9.4), SAS/STAT (13.2, SAS Institute, Cary NC) and/or R (3.1.2).

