For our primary outcome, preliminary data showed that 21.3% of hospital transfers from nursing homes were due to infection. For the probability of transfer due to infection, we assessed the power for a relative reduction of 15%, from 21.3% to 18.1%. Power was estimated at 89% (95% CI [83%, 93%]). For our key secondary outcome of the probability of transfer to a hospital among discharges, our preliminary data showed that 37.8% of discharges were associated with admission to hospitals across the nursing homes. For this outcome, we estimated the power for a relative reduction of 8%, from 37.8% to 34.8%, to be 99.5% (95% CI [97%, 99.9%]). Even at a relative reduction of 5%, we have 74% power (95% CI [67%, 80%]). These effect sizes are meaningful because there is tremendous national interest in reducing preventable readmissions, of which infections are a major cause. Reductions in overall readmissions of 1-3% are lauded as sizeable in the CMS Hospital Readmissions Program which fined 2,225 hospitals in its first year, with each fraction of a percent resulting in substantial lost revenue. The second year of this program saw a reduction of 0.6% in all cause readmissions. In summary, our power assessment demonstrates adequate power to detect plausible and meaningful effects of the proposed trial.

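### The success rule concludes a lower risk of infectious transfer from b3 alone, but b3 shows only a lower infectious share of hospital transfers

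*Combined protocol and SAP*

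**What the plan says.** The final plan's Trial Outcomes table defines the primary outcome as "Hospital transfer due to infection, among hospital transfers". Its Statistical Analysis section sets R to 1 when a transfer carries an infection diagnosis and to 0 otherwise. The model is a logistic mixed model with arm, period, their interaction b3 and a nursing-home random effect. If b3 is negative and significant, "then we can conclude that the intervention reduces the risk of infectious transfer". The original plan has the same sentence and ties trial success to the interaction term.

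The secondary outcome asks: "If the resident was transferred from the nursing home, were they transferred to a hospital". It uses the same kind of model ("All outcomes will be assessed similarly"), but the primary rule does not mention it.

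For power, the plan states "we assessed the power for a relative reduction of 15%, from 21.3% to 18.1" per cent, with estimated power of 89% (95% CI 83% to 93%).

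**The concern.** Residents who are not sent to hospital never enter the primary model. Within it, a lower infectious share can arise because fewer infectious transfers occur, because more non-infectious transfers occur, or from a mixture. The stated conclusion is about the risk of infectious transfer, whose denominator (residents, resident-days or discharges) is not in the model.

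The rule can therefore declare a reduced risk when no infectious transfer was prevented. It can also miss a real benefit: if decolonization lowers both types of transfer in the same proportion, the share does not move. The training module tells staff that the goal is fewer infection-related hospital transfers, so a positive result is likely to be read as a statement about their number.

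**Working it through.** **1. The plan's own figures.** 0.213 × 0.85 = 0.181, as stated. For 200 resamples, 177 rejections (88.5%) give an exact 95% CI of 83.2% to 92.6%, which matches the stated interval. The 89% itself cannot be rebuilt, because the number of transfers per home is not given.

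**2. What b3 measures.** Within a home, the odds of R = 1 are infectious over non-infectious transfers. Let RRi and RRn be the baseline-to-intervention changes in each type, intervention arm relative to control. Any common denominator cancels, so

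b3 = ln(RRi) − ln(RRn), or exp(b3) = RRi / RRn.

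A negative b3 implies RRi < 1 only if RRn < 1/exp(b3). Reading exp(b3) as the size of the effect on infectious transfers needs RRn = 1.

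**3. How large a rise would explain the result.** Planned b3 = logit(0.18105) − logit(0.213) = −0.2023, so 1/exp(b3) = 1.224. The standard error implied by 89% power is 0.2023 / (1.96 + 1.2265) = 0.0635 (0.0694 at 83% power, 0.0589 at 93%). When b3 is only just significant, the bound is exp(1.96 × 0.0635) = 1.133 (1.122 to 1.146). A 13% relative rise in non-infectious transfers would then fully account for it.

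**4. Success with no infectious transfer prevented (RRi = 1).** P(success) = Φ(−1.96 + ln(RRn)/SE).

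- RRn = 1.05: Φ(−1.96 + 0.0488/0.0635) = 11.7% (10-13%). Share = 0.213 / (0.213 + 0.787 × 1.05) = 20.5%.
- RRn = 1.10: Φ(−1.96 + 0.0953/0.0635) = 32.3% (28-37%). Share = 0.213 / (0.213 + 0.787 × 1.10) = 19.7%.
- RRn = 1: 2.5%, the nominal value in this direction.

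**5. Would the secondary outcome warn?** Its baseline is 37.8% of discharges. Its standard error is 0.0812 / (1.96 + 0.643) = 0.0312, from 74% power at a 5% reduction (range 0.0259 to 0.0341 over the stated secondary powers and intervals). Hospital transfers per baseline discharge are T = 0.378 × (0.213 RRi + 0.787 RRn). The answer depends on an assumption of this review: extra transfers either add to discharges, giving T/(T + 0.622), or replace other discharges, giving T.

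| Non-infectious rise | Discharges | Secondary outcome | Significantly raised | Success without that warning |
|---|---|---|---|---|
| +5% | added | 38.7% | 23% (20-32%) | 9% (7-10%) |
| +5% | fixed | 39.3% | 52% (45-68%) | 6% (3-7%) |
| +10% | added | 39.6% | 68% (60-83%) | 10% (5-15%) |
| +10% | fixed | 40.8% | 98% (96-99.8%) | 0.7% (0.1-1.6%) |

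**6. Both types fall by 15%.** b3 = ln(0.85/0.85) = 0, so the primary succeeds 2.5% of the time. The secondary falls to 34.1% (added) or 32.1% (fixed) and detects this with power above 99%.

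**7. Should a second significance test be required?** This was simulated with about 6,100 hospital transfers per arm and period, an assumption chosen to match the standard error. The added condition was that infectious transfers per discharge also be significantly lower.

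| True change (infectious / non-infectious) | Rule as planned | With second test: added / fixed |
|---|---|---|
| 0 / +5% | 12% | 4% / 2.4% |
| 0 / +10% | 33% | 8% / 2.6% |
| Planned b3, non-infectious unchanged | 88% | 87% / 87% |
| −14% / +5% | 89% | 81% / 80% |
| −10% / +10% | 89% | 66% / 51% |

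The 4% and 8% remain in the added case because extra transfers enlarge the number of discharges. The per-discharge odds ratio is then 0.984 or 0.969 although nothing was prevented.

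**The case against.** The strongest reply is that risk of infectious transfer is the plan's shorthand for its defined share. The Power section calls the 21.3% share a probability of transfer due to infection, and R is defined just before the conclusion. On that reading b3 does estimate the right odds. This softens the point, but the sentence as written still goes beyond what b3 shows.

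Second, the key secondary outcome uses the same model, and infectious share times hospital share equals infectious transfers per discharge. The ingredients are therefore planned, and at +10% with fixed discharges the secondary nearly always warns. The Other Outcomes table also lists a per-resident probability of an emergency department transfer for infection. Both help. However, the rule names neither, and the emergency department outcome is reserved for secondary manuscripts.

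Third, the harm is hypothetical. That stands: the documents give no reason to expect more non-infectious transfers under decolonization. A reader might take 12% and 32% as the plan's false-positive rates. They are not. They are conditional on an assumed rise, and with neither type changed the rate is 2.5%.

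A reader might also infer from the toolkits' outcome lines, such as "Transfers due to infection (% of discharges to a hospital due to infection", that the primary denominator is undefined. The documents do not support this: the original plan's design table and the final plan's Trial Outcomes table both define it as hospital transfers.

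**Conclusion.** The point holds as one of interpretation and should be fixed. The primary test is valid for the infectious share of hospital transfers; the written conclusion is wider. The identity in step 2 follows from the model alone. The success probabilities are illustrative: they rest on a normal approximation, the standard error implied by the stated power, and assumed rises in non-infectious transfers. How well the secondary would warn rests on the added-or-fixed assumption about discharges.

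A reader might infer that the trial should succeed only if a second significance test on infectious transfers per discharge is also passed. The figures do not support that. It costs about one point of power or less when non-infectious transfers are unchanged. It costs about 8 to 9 points (−14%/+5%) to 23 to 38 points (−10%/+10%) when true reductions come with a rise in non-infectious transfers, and it does not fully remove the problem in the added case.

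**What to change.** Keep the primary outcome, model and test.

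1. Reword the conclusion: a significant negative b3 supports the statement that the intervention reduces the share (odds) of hospital transfers that are due to infection.
2. Pre-specify, as supporting analyses with the same arm-by-period model, infectious and non-infectious hospital transfers per discharge, each reported with a 95% CI. State that discharges are also counted after randomisation, so this reduces the problem but does not remove it.
3. State that any claim of fewer infectious transfers, or of a lower risk of them, rests on the infectious-per-discharge estimate and its CI, read together with b3 and the all-cause secondary outcome, and not on b3 alone. Do not make a second significance test a condition of trial success.

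The cost is a more cautious headline and two extra models, from counts already needed for the primary and secondary outcomes. The power of the primary test is unchanged.

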## Power

We assessed power via resampling methods. We used preliminary data on outcomes adjusted to an 18-month baseline and intervention period. First, each nursing home was randomly assigned to a study arm. Then, individuals were sampled with replacement from within each nursing home to simulate “baseline” period data. Individuals were sampled again to simulate the “follow-up” period data. For nursing homes assigned to intervention arm, observed readmissions among the sampled follow-up individuals were removed at a given probability to reflect the effect of the intervention. Finally, the analysis planned for the trial was conducted on the resampled “baseline” and “follow-up” data. In this case, the planned analysis is a generalized linear mixed model logistic regression with main effects for period and arm, with the study effect assessed via their interaction, as described above. To estimate power, we repeated this process 200 times. The proportion of times that the null hypothesis of no interaction effect was rejected, with alpha = .05, provided the estimated power. In contrast to analytic approaches to power, we also needed to find confidence limits on the estimate, which we did using exact methods. For cluster-randomized trials, this approach has the advantage that it does not require guessing the value of the intra-class correlation coefficient, or, importantly, its variability. In addition, this approach does not require an assumption of constant cluster size.

For our primary outcome, preliminary data showed that 21.3% of hospital transfers from nursing homes were due to infection. For the probability of transfer due to infection, we assessed the power for a relative reduction of 15%, from 21.3% to 18.1%. Power was estimated at 89% (95% CI [83%, 93%]). For our key secondary outcome of the probability of transfer to a hospital among discharges, our preliminary data showed that 37.8% of discharges were associated with admission to hospitals across the nursing homes. For this outcome, we estimated the power for a relative reduction of 8%, from 37.8% to 34.8%, to be 99.5% (95% CI [97%, 99.9%]). Even at a relative reduction of 5%, we have 74% power (95% CI [67%, 80%]). These effect sizes are meaningful because there is tremendous national interest in reducing preventable readmissions, of which infections are a major cause. Reductions in overall readmissions of 1-3% are lauded as sizeable in the CMS Hospital Readmissions Program which fined 2,225 hospitals in its first year, with each fraction of a percent resulting in substantial lost revenue. The second year of this program saw a reduction of 0.6% in all cause readmissions. In summary, our power assessment demonstrates adequate power to detect plausible and meaningful effects of the proposed trial.

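### The stated powers of 89%, 99.5% and 74% assume that nursing homes do not differ in their underlying change over time, and the analysis model shares that assumption

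*Combined protocol and SAP*

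**What the plan says.** The Power sections of the original and final statistical plans describe the same simulation. The source is a single preliminary data set: "We used preliminary data on outcomes adjusted to an 18-month baseline and intervention period". Homes are assigned to arms at random. Then "individuals were sampled with replacement from within each nursing home to simulate" the baseline period, and "Individuals were sampled again to simulate the" follow-up period. In the intervention arm, "observed readmissions among the sampled follow-up individuals were removed at a given probability to reflect the effect of the intervention". Each simulated trial is analysed with the planned mixed logistic model, and "The proportion of times that the null hypothesis of no interaction effect was rejected, with alpha = .05, provided the estimated power". There were 200 replicates, and the plan adds that "we also needed to find confidence limits on the estimate, which we did using exact methods".

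The plan gives two advantages of resampling: "it does not require guessing the value of the intra-class correlation coefficient, or, importantly, its variability", and "this approach does not require an assumption of constant cluster size". It reports 89% power for the primary outcome (21.3% to 18.1%). For all-cause transfer it reports 99.5% for an 8% relative reduction and 74% for a 5% relative reduction. It concludes that power is adequate.

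The Statistical Analysis section judges the trial by the arm-by-period interaction. The equation there, introduced as a simplified form, has one random term: an intercept for each home.

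**The concern.** On this description, each home has the same underlying rate in both periods, apart from the removed events. Resampling carries real differences between homes in level and in size. Differences in level largely cancel from an arm-by-period interaction, because each home is compared with itself. Differences between homes in how their rate changes do not cancel. They may come from changes in staffing, case mix, coding or referral habits, or from uneven response to the intervention. They add directly to the variance of the estimate, and the simulation sets them to zero. A trend common to all homes is harmless, because the period term absorbs it.

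The random-intercept model makes the same assumption. Data generation and analysis therefore agree with each other, and the simulation had no way to show a problem. Two things are at stake: how much weight the adequacy claim can bear, and whether the interaction test keeps its nominal 5% error.

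**Working it through.** **Inputs from the documents.** 28 homes, 14 per arm (design table, original statistical plan); alpha 0.05, read as two-sided because a 95% CI excluding 0 is the alternative criterion; the rates, powers and 200 replicates above. Home sizes and variation in change are not given. Home sizes are back-solved below and variation in change is assumed over a range.

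**1. The plan's own figures.** 0.213 × 0.85 = 0.181 and 0.378 × 0.92 = 0.348, as stated. Exact limits for 178, 199 and 148 rejections in 200 are 83.8–93.0%, 97.2–99.99% and 67.3–79.9%, which match the plan apart from rounding.

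**2. Do the three powers fit one sample size with no variation in change?** Power = Φ(d/SE − 1.96), with SE² = 3/(n·p1·q1) + 1/(n·p2·q2) and n observations per arm-period.
- Primary: d = logit(0.213) − logit(0.181) = 0.2023. For 89% power, SE = 0.2023/(1.960 + 1.2265) = 0.0635, so n ≈ 6,113 hospital transfers (6,113/14 ≈ 437 per home-period).
- All-cause, 5% effect: d = 0.0812, SE = 0.0312, n ≈ 17,570 discharges. That n gives 98.7% power for the 8% effect (stated 99.5%). It implies 17,570 × 0.378 ≈ 6,640 hospital transfers, hence 91% primary power (stated 89%).

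The three figures are roughly consistent with binomial error alone. This fits the assumption but does not prove it.

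**3. Add home-by-period variation.** Let s be the SD of each home-period's log odds about its home level. The interaction is a contrast of four means over 14 homes each, so SE_total² = SE² + 4s²/14. The SD of a home's change is √2·s = 1.41s.

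Example, s = 0.10: 0.00403 + 0.00286 = 0.00689, so SE_total = 0.0830.
- Test whose SE includes the variation: Φ(0.2023/0.0830 − 1.96) = 68%.
- Planned test (uses 0.0635 when the true SE is 0.0830): type I error 2Φ(−1.96 × 0.0635/0.0830) = 13%; rejection under the effect Φ((0.2023 − 1.96 × 0.0635)/0.0830) = 83%.

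Primary outcome:

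| s | SD of change (log odds; points around 21.3%) | Planned test: rejection | Planned test: type I error | Approximately 5% test: normal | Same, 26 df |
|---|---|---|---|---|---|
| 0 | 0 | 89% | 5% | 89% | 87% |
| 0.05 | 0.07; 1.2 | 87% | 7% | 84% | 81% |
| 0.10 | 0.14; 2.4 | 83% | 13% | 68% | 65% |
| 0.15 | 0.21; 3.6 | 78% | 22% | 51% | 48% |

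At s = 0.02 the figures are 88% (normal) and 5.3% type I error. Power of the approximately 5% test falls below 80% at s of about 0.053 (26 df) to 0.064 (normal), an SD of change of about 1.3 to 1.5 points.

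**4. Check with models fitted.** Simulation used 28 equal homes, unpaired, an assumed intercept SD of 0.3, event removal with probability 0.15 and 1,000 replicates per cell (Monte Carlo SE at most 1.6 points). At s = 0/0.05/0.10/0.15 the random-intercept model rejects 89/89/84/80% under the effect and 6/7/13/21% under the null. A home-by-period model on 26 df gives 86/84/70/52% and 4/4/6/6%. An assumed size CV of 0.5 gives a similar picture. These error rates are two-sided. In a separate run at an SD of change of 0.10, 6.3 of 11.7 points lay in the direction of benefit.

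**5. All-cause transfer, approximate.** Each effect is back-solved from its own 200-replicate power (SE 0.0312 and 0.0288), and one set of homes cannot support both exactly. At s = 0.05 and 0.10 the approximately 5% test has 51% and 26% power for the 5% effect, and 91% and 58% for the 8% effect. Planned-test type I error is about 14–15% and 32–35%.

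**6. Pairing.** The Randomization section of the original plan contemplates matched pairs. If changes correlate ρ within pairs, the added term is 4s²(1 − ρ)/14. At s = 0.10, primary power is 74% (ρ = 0.3) or 78% (ρ = 0.5) instead of 68%.

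**The case against.** - **The plan defines power as the rejection rate of its own planned analysis.** On that definition the primary figure is fairly stable up to s of about 0.10, staying at or near the stated 83–93%. This stands. The falls to 68% and 51% belong to a test the plan does not propose. But the planned test's rejection rate holds up only because its type I error rises.
- **The model is introduced as a simplified form, so the fitted model may be richer.** That is possible. The only random effect described is the home intercept, and every type I figure for the planned test depends on that reading.
- **s has no anchor in the documents.** True: the consequence runs from trivial to serious with the chosen value. A reader might infer that the trial is underpowered or that 89% is wrong. The documents support neither reading. They show only that the figures rest on an unstated assumption.
- **The exact limits match the stated powers.** A reader might take this as evidence for zero variation in change. It is not. Any data-generating model giving the same rejection counts in 200 replicates gives the same limits, which measure Monte Carlo error only.
- **The test described as valid is not exact.** In simulation, the home-by-period model rejected 7% under the null for all-cause transfer at s = 0.05, so it holds 5% only approximately.
- **The intervention ended in December 2018, before the final plan was dated.** The number of homes cannot change. The analysis model and the stated conclusion on power still can.

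**Conclusion.** The point holds as an unstated modelling assumption, not as an arithmetic error. The stated 89%, 99.5% and 74% assume that homes do not differ in underlying change, and the interaction test as written assumes the same. Over s = 0 to 0.15, planned-test type I error on the primary outcome runs from about 5% to 22%. Power of a test that approximately holds 5% runs from about 89% to 51%, or 2–3 points lower on 26 df. All-cause transfer is more sensitive, but its figures are approximate.

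This rests on four things: one preliminary pool per home, inferred because no other source is described; a random intercept as the only random effect; equal home sizes back-solved from the stated power; and an assumed range for s. If homes were paired and changes correlate within pairs, less is lost. At s of 0.02 or less the primary outcome is barely affected. Confidence is medium, and the plan should be corrected.

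**What to change.** 1. **Statistical Analysis.** Test the arm-by-period interaction with a home-by-period random effect and a small-sample reference such as 26 df, or with a weighted home-level analysis of change.
2. **Power.** Repeat the simulation with home-by-period variation in the data and the matching term in the model, carrying any pairing used at randomisation. Estimate the variance, beyond binomial error, from baseline data split by calendar period if possible; otherwise use a stated range such as s = 0 to 0.15. Restate power for both outcomes as a range with simulated type I error beside it, and say that the exact limits reflect 200 replicates only.
3. **Intra-class correlation sentence.** Keep it, but say that resampling covers between-home differences in level, not in change.

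The cost is a few hours of simulation and a less favourable stated power; no homes are added. If change does not vary, the new term costs about 2 to 4 points of primary power. If it does vary, the interval widens. The home-level option should be weighted: an unweighted t test gave 76% with no variation in change and an assumed size CV of 0.5. If the variance cannot be estimated, the sensitivity range alone still corrects the record.

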## Summary of Goals

Nursing homes frequently admit large numbers of residents harboring highly antibiotic-resistant bacteria known as multi-drug resistant organisms (MDROs). These MDROs can cause serious infections and outbreaks. Large clinical trials in hospitals have proven that removal of these bacteria from the skin and nares using antiseptic soaps and ointments (decolonization) can prevent MDROs and infections.

This trial will compare routine bathing care to body surface decolonization to not only achieve the known benefits of MDRO reduction, but to assess whether decolonization may also reduce antibiotic use and hospitalization due to infection.

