# What is Project PROTECT?

- This trial is evaluating whether bathing with special antiseptic soap plus using nasal products to remove nose bacteria (universal decolonization) is better than routine bathing in nursing homes in reducing infection and antibiotic-resistant bacteria
- The goal is to:
  - Reduce transfers to hospitals due to infections
  - Reduce antibiotic use
  - Reduce multi-drug resistant organisms (MDROs)
- The 28 Southern California nursing homes participating in this trial will be randomized to one of the following groups:
  - **Group 1: Routine Care**
  - **Group 2: Universal Decolonization**
- Intervention begins **April 2017**

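### Does the plan claim adequate power too broadly for all-cause hospital transfers, given the small readmission reductions that it cites?

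*Combined protocol and SAP*

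**What the plan says.** The Power section of the final statistical plan repeats that of the original plan. Power was estimated by resampling preliminary data 200 times and fitting the planned mixed logistic model. The share of runs that rejected the null for the arm-by-period interaction, "with alpha = .05, provided the estimated power".

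Three powers are given:

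- Primary outcome, infectious share of hospital transfers: 89% (CI 83-93%) for a 15% relative fall, 21.3% to 18.1%.
- Key secondary outcome, hospital transfer among discharges: 99.5% (CI 97-99.9%) for an 8% relative fall, 37.8% to 34.8%.
- The same secondary outcome at a smaller effect: "Even at a relative reduction of 5%, we have 74% power (95% CI [67%, 80%]).

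The plan then calls these effect sizes meaningful because preventable readmissions are of national interest. It adds that "Reductions in overall readmissions of 1-3% are lauded as sizeable in the CMS Hospital Readmissions Program" and that "The second year of this program saw a reduction of 0.6% in all cause readmissions". It does not say whether these figures are relative changes or percentage points. The section ends with the conclusion that "our power assessment demonstrates adequate power to detect plausible and meaningful effects of the proposed trial".

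**The concern.** The closing sentence covers both outcomes alike. For all-cause transfers, the smallest effect examined already has less than the customary 80% power, and no minimum detectable effect is given. The only outside figures offered are 1-3% and 0.6%. They suggest that falls smaller than 5% would matter, and they do not show that 5% or 8% is plausible. A reader could conclude that the trial is well powered for falls of 1-3% and later read a non-significant all-cause result as evidence against them.

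A second strand comes from the trial's stated aim, which the training material gives as "Reduce transfers to hospitals due to infections". If only infectious transfers were prevented, the all-cause fall that goes with the primary effect would be smaller than either all-cause effect examined.

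**Working it through.** **Inputs.** All come from the final plan's Power and Statistical Analysis sections: a control rate of 37.8%; 74% power at a 5% relative fall; 99.5% at 8%; alpha 0.05. The test is taken as two-sided, because the decision rule equates its p-value with a 95% interval: "If it is negative with p-value < .05 (or 95% CI excluding 0". Discharge counts and home sizes are not given, so the simulation cannot be rerun. The standard error is instead back-solved from each stated power.

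**The plan's own figures.** 37.8% × 0.92 = 34.8% and 21.3% × 0.85 = 18.1%, as stated. Exact 95% limits for 200 runs are 67.3-79.9% for 148 rejections (74%), 97.2-99.99% for 199 (99.5%) and 83.8-93.0% for 178 (89%). These match the printed intervals apart from rounding.

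**Implied standard error.** SE = |log odds ratio| / (1.960 + z for the stated power).

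- 5% fall, 37.8% to 35.91%: log odds ratio 0.0812; SE = 0.0812 / (1.960 + 0.643) = 0.0312.
- 8% fall, 37.8% to 34.78%: log odds ratio 0.1309; SE = 0.1309 / (1.960 + 2.576) = 0.0289.

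The first SE predicts 98.7% power at 8% (stated 99.5%). The second predicts 80.4% at 5% (stated 74%, upper limit 80%). The two figures agree to within about the simulation error of 200 runs.

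**Effect with 80% power.** Power = Φ(|log odds ratio|/SE − 1.960) + Φ(−|log odds ratio|/SE − 1.960). Solving for 80% gives a 5.4% relative fall (2.0 points) from the first SE and 5.0% (1.9 points) from the second. Over the stated confidence intervals the range is 4.5-5.9% (1.7-2.2 points).

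**Power at the cited reductions, on each possible scale:**

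| Reduction | Read as relative | Read as percentage points |
|---|---|---|
| 0.6 | 6% | 13-14% |
| 1 | 8-9% | 28-32% |
| 2 | 18-20% | 79-85% |
| 3 | 34-39% | 99% |

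Each range runs from the first SE to the second. At the extreme of the stated intervals, a 3% relative fall reaches about 47%.

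**The tested effects in points.** 37.8 × 0.05 = 1.9 and 37.8 × 0.08 = 3.0. If the readmission figures are percentage points, both tested effects lie within 1-3.

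**Infection-only scenario.** Suppose non-infectious transfers and total discharges do not change. Moving the infectious share from 21.3% to 18.1% then requires preventing 1 − (0.18105 × 0.787)/(0.213 × 0.81895) = 18.3% of infectious transfers. The all-cause fall is 0.213 × 0.183 = 3.9%, with 53-59% power from the two SEs.

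**The case for a change.** The best argument for a change is that the plan chose these benchmarks itself. If they do not carry over to nursing homes, nothing quantitative supports the word plausible for this outcome. If they do, power over much of the cited range is low. All-cause transfer is also the only secondary outcome left after antibiotic use was removed, and the rewording would cost one sentence.

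Part of this stands. The scale of the readmission figures is unstated, no evidence is given that a 5% or 8% fall is likely, and the conclusion is phrased more generally than two tested effects warrant.

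The rest does not carry. The readmission figures follow directly on the statement that the tested effects are meaningful. The reasoning is that if reductions of that order are valued, effects of the tested size are worth finding. They are not presented as design targets, and no power is claimed for them. They also concern hospital readmissions in a national programme, with different events and a different denominator, so power at those values is the reader's construction. The 80% threshold is a convention; the plan sets no target power. The infection-only scenario needs non-infectious transfers and total discharges to stay unchanged and both planned effects to arise together. The plan powers the two outcomes separately and assumes none of this.

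**Conclusion.** No change to the plan is called for. The stated powers of 89%, 99.5% and 74% are not in error, and the 74% stands in the same paragraph as the conclusion, so a reader can see that power drops below 80% near a 5% relative fall. What remains is a minor point of wording about a secondary outcome: 80% power is reached only from about 5.0-5.4% relative (1.9-2.0 points; 4.5-5.9% over the stated intervals). If the cited reductions are relative, all have under 40% power on the point estimates. If they are points, 0.6 and about the lower half of 1-3 fall below 80%.

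A narrower sentence would leave the outcomes, model, number of homes, decision rule and results as they are. The final plan is dated August 2019, after the intervention period ended in December 2018, so it could not affect the design either. If the all-cause result is not significant, its confidence interval will show which reductions remain compatible with the data, and an analyst would rely on that rather than on the summary sentence.

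The figures rest on a normal approximation, a two-sided 5% test and standard errors back-solved from 200-run estimates. The resampling draws both periods from the same preliminary data for each home. If homes drift differently between periods, true power would be lower than stated and the detectable effect larger.
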